* From IFUs for FlowTriever Catheter (LB-0047 RevJ), Triever 16 (LB-0060 RevL), Triever 20 (LB-0139 RevM), Triever 20 Curve (LB-0144 RevJ), and Triever 24 (LB-0151 RevE)

TABLE A2: KNOWN RISKS FOR CATHETER-DIRECTED THROMBOLYSIS**

Event Category	Event
Cardiac	Arrhythmia
	Right bundle branch block and complete heart block
	Hypotension
	Tricuspid and pulmonic valve damage
	Intimal disruption
Wound	Hematoma
Peripheral vascular	Vessel perforation
	Arterial dissection
	Arteriovenous fistula
	Thromboembolic episodes
	Thrombophlebitis
	Distal embolization
	Vessel spasm
Venous	Vascular thrombosis
	Cholesterol embolization
	Thromboembolism
Cerebrovascular	Intracranial hemorrhage
Pulmonary	Perforation of the pulmonary artery
	Pulmonary re-embolization
	Pulmonary edema
	Pleural effusion
	Pneumothorax
	Pulmonary infarct due to tip migration and spontaneous wedging, air embolism, and/or thromboembolism
Miscellaneous	Hemorrhage
	Contrast extravasation
	Pain and tenderness
	Sepsis/Infection
	Drug reactions
	Allergic reaction to contrast medium
	Orolingual angioedema
	Neurological deficits including stroke and death
	Amputation
	Death

** From EKOS Endovascular System product brochure (PI-726201-AA), Label for Activase (Reference ID: 3702389),
Uni-Fuse Product information (<https://www.angiodynamics.com/about-us/risk-information>)

ICU	Intensive Care Unit
ISTH	International Society on Thrombosis and Haemostasis
ITT	Intention To Treat
LMWH	Low molecular weight heparin
LV	Left ventricle
mMRC	Modified Medical Research Council Dyspnea Scale
PA	Pulmonary Artery
PE	Pulmonary Embolism
PEmb-QOL	Pulmonary Embolism Quality of Life
PESI	Pulmonary Embolism Severity Index
PP	Per Protocol
RV	Right ventricle
RV/LV	Right ventricular to left ventricular diameter ratio
sPESI	Simplified Pulmonary Embolism Severity Index
VTE	Venous thromboembolism

PROPRIETARY AND CONFIDENTIAL

The information contained in this document is the sole property of Inari Medical

	PEERLESS Study: Statistical Analysis Plan	Version 5.0 March 22, 2024 Page 8 of 25
---	--	---

1. Description of Study Objectives

The primary study objective is to compare the clinical outcomes of patients treated with the FlowTriever (FT) System versus catheter-directed thrombolysis (CDT) for use in the treatment of acute pulmonary embolism (PE).

2. Study Design

The PEERLESS study is a prospective, multicenter, open-label, randomized controlled trial of the FlowTriever System compared to CDT for acute PE, and includes a non-randomized cohort for subjects with an absolute contraindication to thrombolytics. The study will collect data on demographics, comorbidities, details from the PE diagnosis and treatment, and clinical outcomes through 30-day follow up. The follow up evaluations will include the 24-hour visit (24 hours \pm 8 hours), hospital discharge, and the 30-day/Exit visit (30 days +15 days). All windows reference time from Index Procedure completion (defined as time of exit from the procedure room).

2.1. Study Population

Randomized Controlled Trial Cohort (RCT Cohort):

Up to 550 subjects with acute PE will be enrolled and randomized at up to 60 study sites in US, EU, and/or UK. All subjects who sign informed consent and who meet all of the inclusion criteria and none of the exclusion criteria will be randomized (1:1, FlowTriever or CDT). The inclusion and exclusion criteria are described in sections 2.3 and 2.4.

- One-to-one (1:1) randomization will be stratified by bleeding risk, as measured by the VTE-BLEED score¹. The detailed algorithm for computing VTE-BLEED score is described in Table 1 of the study protocol.
- Stratification by the VTE-BLEED algorithm will occur automatically in the Electronic Data Capture (EDC) system upon data entry, and randomization will be assigned accordingly.

Non-Randomized Absolute Contraindication to Thrombolytics Cohort (Contraindication Cohort):

Up to 150 additional subjects who meet study eligibility criteria and who have an absolute contraindication to thrombolytics, whose initial planned primary treatment strategy includes FlowTriever, will be evaluated as part of the Contraindication Cohort. The same RCT Cohort clinical assessments and follow up schedule will be administered in this Contraindication Cohort.

PROPRIETARY AND CONFIDENTIAL

The information contained in this document is the sole property of Inari Medical

	PEERLESS Study: Statistical Analysis Plan	Version 5.0 March 22, 2024 Page 9 of 25
---	--	---

2.2. Point of Enrollment

To participate in the study, the patient must sign the informed consent. If a subject signs the informed consent but is later deemed NOT to meet the invasive systolic PA pressure eligibility criteria, the subject would be considered a screen failure and not enrolled in either the RCT Cohort or the Contraindication Cohort. Screen failures will be tracked in the EDC system with rationale for the screen failure. The point of enrollment is when the subject meets all eligibility criteria and study device enters the subject's body. If the index catheter-based intervention procedure is aborted before treatment catheter insertion or is not performed, the subject is considered a screen fail.

Enrollment considerations in study design

Any patient with a documented ***absolute contraindication*** to thrombolytics will be excluded from the RCT Cohort but may be enrolled in the Contraindication Cohort if treated with FlowTriever. Absolute contraindications include (per ESC Guidelines 2019² and AHA Scientific Statements 2019):

- History of hemorrhagic stroke or stroke of unknown origin
- Ischemic stroke in previous 6 months
- Presence of intracranial conditions that may increase the risk of bleeding, such as neoplasms, arteriovenous malformations, or aneurysms
- Recent (within 3 months) intracranial or intraspinal surgery or serious head trauma
- Bleeding diathesis
- Active internal bleeding, excluding menses
- Aortic dissection
- Severe uncontrolled hypertension
- Any other condition listed as an absolute contraindication on the product label for the thrombolytic agent planned for use by local standard and investigator discretion

Subjects with a ***relative contraindication*** to thrombolytics are eligible for the RCT Cohort per protocol. Subjects with only relative contraindication(s) to thrombolytics are not eligible for the Contraindication Cohort. Relative contraindications include:

- Transient ischemic attack in previous 6 months
- Oral anticoagulation, except for aspirin
- Therapeutic LMWH within 24 hours
- Pregnancy or first post-partum week
- Non-compressible puncture sites
- Traumatic resuscitation, defined as prolonged (>10 min) cardiopulmonary resuscitation

[figure not shown]
PROPRIETARY AND CONFIDENTIAL

The information contained in this document is the sole property of Inari Medical

- Refractory hypertension (systolic BP >180 mmHg or diastolic BP >110 mmHg) on two confirmed measurements
- Advanced liver disease
- Infective endocarditis
- Active peptic ulcer
- Recent administration of glycoprotein (GP) IIb/IIIa inhibitors
- Anemia (e.g. hemoglobin <10 g/dL)

Figure 1 summarizes the enrollment process which will be implemented in this study.

Figure 1 Subject Enrollment Flowchart

PROPRIETARY AND CONFIDENTIAL

The information contained in this document is the sole property of Inari Medical

	PEERLESS Study: Statistical Analysis Plan	Version 5.0 March 22, 2024 Page 11 of 25
---	--	--

2.3. Inclusion Criteria

Subjects must meet each of the following criteria to be included in the study:

1. Age \geq 18 years
2. Echo, computed tomographic pulmonary angiography (CTPA), or pulmonary angiographic evidence of any proximal filling defect in at least one main or lobar pulmonary artery
3. Including ALL of the following:
 - a. Clinical signs and symptoms consistent with acute PE, or PESI class III-V, or sPESI \geq 1
AND
 - b. Hemodynamically stable
AND
 - c. RV dysfunction on echocardiography or CT
AND
 - d. Any one or more of the following present at the time of diagnosis:
 - i. Elevated cardiac troponin levels
 - ii. History of heart failure\
 - iii. History of chronic lung disease
 - iv. Heart rate \geq 110 beats per minute
 - v. SBP $<$ 100mmHg
 - vi. Respiratory rate \geq 30 breaths per minute
 - vii. O₂ saturation $<$ 90%
 - viii. Syncope related to PE
 - ix. Elevated lactate
4. Intervention planned to begin within 72 hours of the later of either
 - a. Confirmed PE diagnosis
OR
 - b. If transferring from another hospital, arrival at the treating hospital
5. Symptom onset within 14 days of confirmed PE diagnosis

2.4. Exclusion Criteria

Subjects will be excluded from the study for any of the following criteria:

1. Unable to anticoagulate with heparin, enoxaparin or other parenteral antithrombin
2. Index presentation with hemodynamic instability that are part of the high-risk PE definition in the ESC Guidelines 2019², including ANY of the following:
 - a. Cardiac arrest
OR

PROPRIETARY AND CONFIDENTIAL

The information contained in this document is the sole property of Inari Medical

	PEERLESS Study: Statistical Analysis Plan	Version 5.0 March 22, 2024 Page 12 of 25
---	--	--

- b. Systolic BP < 90 mmHg or vasopressors required to achieve a BP \geq 90 mmHg despite adequate filling status, AND end-organ hypoperfusion
OR
- c. Systolic BP < 90 mmHg or systolic BP drop \geq 40 mmHg, lasting longer than 15 min and not caused by new-onset arrhythmia, hypovolemia, or sepsis
- 3. Known sensitivity to radiographic contrast agents that, in the Investigator's opinion, cannot be adequately pre-treated
- 4. Imaging evidence or other evidence that suggests, in the opinion of the Investigator, the patient is not appropriate for catheter-based intervention (e.g. inability to navigate to target location, clot limited to segmental/subsegmental distribution, predominately chronic clot)
- 5. Patient has right heart clot in transit identified at baseline screening
- 6. Life expectancy < 30 days (e.g. stage 4 cancer or severe COVID-19 infection), as determined by the Investigator
- 7. Current participation in another drug or device study that, in the investigator's opinion, would interfere with participation in this study
- 8. Current or history of chronic thromboembolic pulmonary hypertension (CTEPH) or chronic thromboembolic disease (CTED) diagnosis, per ESC 2019 guidelines²
- 9. Invasive systolic PA pressure \geq 70mmHg prior to study device entering the body
- 10. Administration of bolus or drip/infusion thrombolytic therapy or mechanical thrombectomy for the index PE event within 48 hours prior to enrollment
- 11. Ventricular arrhythmias refractory to treatment at the time of enrollment
- 12. Known to have heparin-induced thrombocytopenia (HIT)
- 13. Subject has any condition for which, in the opinion of the investigator, participation would not be in the best interest of the subject (e.g., compromise the well-being or that could prevent, limit, or confound the protocol-specified assessments). This includes a contraindication to use of FlowTriever or CDT System (for example, EKOS System) per local approved labeling
- 14. Subject has previously completed or withdrawn from this study
- 15. Patient unwilling or unable to conduct the follow up visits per protocol

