^f Imaging can be either echo or CT, but needs to be the same modality within each patient at Baseline and 24-hour visit

^g Note that the evaluation of endpoint considerations include All-cause mortality, ICH, Major bleeding, Clinical deterioration and/or escalation to a bailout therapy, and ICU admission and ICU length-of-stay. These are assessed at hospital discharge or 7 days after the index procedure, whichever is earlier. If a subject is still in the hospital and exits the study for any reason before the 30-day Visit, evaluation of primary endpoint components should be completed at the time of patient exit.

^h The Index Procedure begins when access for treatment is obtained. The Index Procedure is considered complete upon exit from the procedure room. The time of exit from the procedure room is the time reference used for the subsequent visit windows including the 24-hour visit.

BASELINE ASSESSMENTS

The baseline assessments must be done \leq 72 hours of Index Procedure including:

- Informed consent
- Inclusion/exclusion review
- Demographics
- Medical history, risk factors, and PE condition
- Anticoagulation regimen
- Clinical labs (Hemoglobin, Troponin)
- Cardiac imaging (Echo or CT)
 - Imaging can be either echo or CT, but needs to be the same modality within each patient at baseline and 24-hour visit.
- mMRC dyspnea score, Borg, and NYHA

ALLOCATION AND RANDOMIZATION

Upon the patient meeting baseline eligibility criteria and providing informed consent, a check against the list of absolute contraindications to thrombolytics is performed (see Figure 9: Patient Enrollment Flowchart). Subjects with one or more absolute contraindications to thrombolytics and whose initial treatment plan includes FlowTriever are allocated to the Contraindication Cohort. Subjects without any absolute contraindications (whether there are relative contraindications to thrombolytics or no contraindication to thrombolytics) are allocated to the RCT Cohort.

Study sites will receive the subject randomization assignment electronically in the electronic data capture (EDC) system upon completion of baseline information used to stratify randomization using the calculated VTE-BLEED score. Subjects will be randomized to and treated with (a) mechanical thrombectomy with FlowTriever or (b) catheter-directed thrombolysis per local practice standards.

INDEX PROCEDURE

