The initial catheter-based intervention for acute PE is considered the Index Procedure. The procedure is conducted under fluoroscopic/angiographic guidance. Refer to the Instructions for Use (IFU) for techniques and methods for device deployment. The following assessments are collected during the index procedure including:

- Anticoagulation regimen
- Clinical labs (Hemoglobin, ACT, and PTT collected just prior to index procedure intervention)
- Oxygenation status collected just prior to index procedure
- Invasive PA pressures (**required** pre-index procedure)
 - Interventionalists will collect pulmonary artery pressures immediately before primary therapeutic catheter insertion.
- Invasive PA pressures (**optional** post-index procedure)
 - Trained interventionalists will collect pulmonary artery pressures at least 10 minutes after primary therapeutic catheter (for CDT) begins therapy, or after the primary therapeutic catheter (for FlowTriever) is removed for the last time. Additional PA pressures are requested to be collected in the CDT subjects 6 hours (\pm 2 hours) post procedure using the same technique.
- Bleeding measures
- Adverse event assessment

The Index Procedure begins when access for treatment is obtained. The Index Procedure is considered complete upon exit from the procedure room. The time of exit from the procedure room is the time reference used for the subsequent visit windows including the 24-hour visit. The 7-day maximum for in-hospital primary endpoint

assessment is defined as 168 hours from the end of the Index Procedure. The 30-day Visit window refers to 30 calendar days from the day the Index Procedure ends.

Recommendations for Anticoagulation Management and Thrombolytic Therapy

In order to approximate real-world practice, the use of pre-procedure, intra-procedure, and post-procedure anticoagulation should be guided by investigator discretion, local standard of care, and in accordance with IFU for the assigned therapy.

Similarly, dose and duration of thrombolytic agents in subjects assigned to CDT is guided by investigator discretion, local standard of care, and in accordance with IFU. Initial dosing strategy should be recorded in the corresponding CRF, along with any changes in dose throughout the infusion, including extended infusion times. Bolus thrombolytics that are part of initial treatment plan are not considered bailout, although bolus lytics are discouraged in subjects assigned to FlowTriever therapy.

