3.1. Intention To Treat Population

All subjects who met the inclusion/exclusion criteria, provided informed consent, and who were randomized to the FlowTriever or CDT group will be included in ITT. To be included in ITT, subjects must receive some treatment for PE after randomization. This study will consist of up to 550 subjects with acute PE who meet the eligibility criteria, and are enrolled, consented, and randomized. Subjects will be excluded from ITT population if no treatments were given, or no data were available after randomization.

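### Exclusions 10 and 11 are timed to device entry, after the open-label assignment, so an event after randomisation can make a randomised subject ineligible and may remove that subject from ITT

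*SAP*

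**What the plan says.** Four statements matter, and they stand in different places.

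- **The clock.** Exclusion 10 (Protocol 6; SAP 2.4) covers "Administration of bolus or drip/infusion thrombolytic therapy or mechanical thrombectomy for the index PE event within 48 hours prior to enrollment". Exclusion 11 covers "Ventricular arrhythmias refractory to treatment at the time of enrollment".
- **What enrollment means.** SAP 2.2, like Protocol 6 (Point of Enrollment), states: "The point of enrollment is when the subject meets all eligibility criteria and study device enters the subject's body".
- **When the arm is known.** Protocol 7 (Allocation and Randomization): "Study sites will receive the subject randomization assignment electronically in the electronic data capture (EDC) system upon completion of baseline information". SAP 2 describes the study thus: "The PEERLESS study is a prospective, multicenter, open-label, randomized controlled trial of the FlowTriever System compared to CDT for acute PE".
- **Who is analysed.** SAP 3.1 starts from "All subjects who met the inclusion/exclusion criteria, provided informed consent, and who were randomized". It then adds that a subject must have had some PE treatment after randomisation, and it names absence of treatment or of data as grounds for exclusion.

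Two further rules bear on the point. Protocol 7 (Withdrawals and Lost to Follow Up) and SAP 2.2 class a subject as a screen failure if the procedure is not done or stops before the treatment catheter goes in. Protocol 7 (Recommendations for Anticoagulation Management and Thrombolytic Therapy) says: "Bolus thrombolytics that are part of initial treatment plan are not considered bailout", and discourages such boluses in FlowTriever subjects.

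**The concern.** Eligibility should be fixed by facts that exist before the arm is known. Here two exclusion criteria stay open until the study device enters the body. Site staff know the assignment by then, and the patient may have worsened or been treated in the meantime. A thrombolytic given in that interval, or a refractory ventricular arrhythmia at its end, is a post-randomisation event that the criteria treat as a baseline fact.

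If such subjects are then left out of ITT, the primary comparison is no longer between the groups as randomised. This differs from the rule in SAP 3.1 on subjects with no treatment or no data: these subjects may have been treated and have data, and only the eligibility clock would remove them. Should the interval, or the use of lytics within it, differ between arms, the win ratio would be biased.

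**Working it through.** No figure in the plan depends on this point. The required 432 subjects (216 per arm) cannot be reproduced, because the component event rates are not stated. The check is therefore a reading of the sequence, followed by an illustration under assumed rates.

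**1. Order of events.** The arm is released when the stratification data are complete (Protocol 7). The device to be inserted depends on the arm, so assignment must precede device entry, which is enrollment. The documents set no limit on the gap. The 72 hours in inclusion criterion 4 run from diagnosis or transfer arrival, not from assignment.

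**2. Two routes out of the comparison.**
- *Device inserted anyway.* Lysis within the preceding 48 hours meets exclusion 10; refractory arrhythmia at that moment meets exclusion 11. The subject then fails the first condition of SAP 3.1. Lysis more than 48 hours earlier, or an arrhythmia controlled by then, triggers neither.
- *No catheter inserted.* The screen-failure rule applies, whatever exclusions 10 and 11 say.

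**3. What a retained subject would contribute.** Under Protocol 5, deterioration must be new since enrollment, and bailout requires that the assigned strategy has been started. A pre-device event would therefore generally not count in the fourth tier (deterioration or bailout). Death, intracranial haemorrhage, major bleeding and ICU stay in the endpoint window would count.

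**4. Illustration (all rates assumed).** Same outcome distribution in both arms: death 1%, ICH 0.5%, major bleeding 5%, deterioration/bailout 4%, ICU over 24 h 30%, ICU 0–24 h 34.5%, no ICU 25%. Treated as exclusive ordered categories:
- tie share = sum of squared proportions = 0.27575
- P(win) = P(loss) = (1 − 0.27575)/2 = 0.362125

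Let a fraction q of the FlowTriever arm have a pre-device event. If these subjects are removed, the win ratio is 1.00. If they are kept and scored in tier 4, they beat 0.01 + 0.005 + 0.05 = 0.065 of CDT subjects and lose to 0.30 + 0.345 + 0.25 = 0.895:

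WR = [(1 − q) × 0.362125 + 0.065q] / [(1 − q) × 0.362125 + 0.895q]

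If they are kept and the pre-device event is not counted, but each has an ICU stay over 24 h, 0.065 becomes 0.105 and 0.895 becomes 0.595.

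| q (of 275) | Removed | Kept, scored tier 4 | Kept, scored ICU > 24 h |
|---|---|---|---|
| 2% (5.5) | 1.00 | 0.3562/0.3728 = 0.955 | 0.3570/0.3668 = 0.973 |
| 5% (13.75) | 1.00 | 0.3473/0.3888 = 0.893 | 0.3493/0.3738 = 0.934 |

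If the events fall in the CDT arm instead, the tier-4 figures invert to 1.047 and 1.120. If retained subjects have the same outcomes as everyone else, keeping or removing them makes no difference on average. By step 3, the tier-4 column is an upper-bound illustration of what the pre-device event itself could do. A subject who later dies or bleeds would score worse, on account of that later event.

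**5. Type I error, same assumptions.** F-S test, 275 per arm, one-sided 0.025, 4,000 simulated trials per scenario (Monte Carlo standard error √(0.025 × 0.975/4000) ≈ 0.0025), events equally frequent in both arms and scored in tier 4 when kept:
- removed in both arms: 0.025 at 2%, 0.023 at 5%
- removed in the FlowTriever arm only: 0.051 at 2%, 0.133 at 5%

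The second line shares the upper-bound scoring and adds one-arm removal, which no document suggests.

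**The case against.** The strongest reply is that eligibility is meant to be settled at baseline. Protocol 6 and SAP 2.1 say that subjects who meet all the criteria will be randomised, and the schedule marks eligibility review at baseline only. The only later check named is invasive PA pressure. The enrollment flowchart is not available in the text, so the sequence is inferred. This stands as a likely intention, but it does not move the clock written into exclusions 10 and 11, and the PA pressure check shows that eligibility can stay open until the procedure.

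A second reply is that removal from ITT is not certain. The sentence in SAP 3.1 that names exclusions lists only no treatment or no data, and rescue lysis is a PE treatment. Protocol 11 treats departures from the eligibility criteria as protocol deviations. SAP 3.2 makes deviations and non-assigned treatment reasons for leaving the per-protocol set, which is a subset of ITT. This stands too: the documents conflict and do not settle the matter.

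A reader might go further and infer three things that the documents do not support:
- *That the rule favours FlowTriever.* Nothing shows that such events or removals differ by arm, and the direction reverses with the arm affected.
- *That planned boluses trigger exclusion 10 in the CDT arm alone.* The bolus sentence is an endpoint rule about bailout and does not say when the bolus is given. A planned bolus before catheter entry could meet exclusion 10, mainly but not only in CDT subjects, because boluses are discouraged rather than barred with FlowTriever.
- *That those removed are the sickest subjects, or wait up to 72 hours after assignment.* Neither is stated.

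**Conclusion.** The concern holds as a defect of timing and an unresolved conflict. Read with SAP 3.1, exclusions 10 and 11 allow a randomised subject to be dropped from ITT because of a thrombolytic given before device entry, or a refractory arrhythmia at device entry. Other passages would keep that subject. Who belongs in the primary analysis should not be left to judgement after an open-label assignment.

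The size is unknown. Removal at equal rates in both arms leaves type I error near nominal, though it changes the population analysed. Removal that differs by arm biases the win ratio in either direction. The shifts shown for 2% and 5% rest on assumed rates and upper-bound scoring; they are not estimates for this trial. The increase from 432 to 550 subjects (118, or 21.5% of 550) can absorb lost precision but does not protect against bias of this kind. A correction is worth making because it is cheap and because a retained subject's deaths, bleeds and ICU stay inform the comparison.

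**What to change.** 1. In Protocol 6 and SAP 2.4, assess exclusions 10 and 11 at randomisation, for eligibility status and the analysis set.
2. In SAP 3.1, state that events or treatments after randomisation do not make a subject ineligible and do not remove the subject from ITT. Reconcile this with SAP 2.1, 2.2 and 2.4 and with Protocol 6.
3. In Protocol 7 and SAP 2.2, provide that a randomised subject whose procedure is aborted or not performed is not reclassified as a screen failure for the ITT analysis. Without this, re-timing the two criteria leaves the second route open.
4. State the time origin of the endpoint window for such a subject. The present origin, the end of the Index Procedure, does not exist if there was no procedure.
5. Clarify how a planned bolus given before catheter entry stands against exclusion 10.

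Whether the procedure goes ahead stays with the treating physician; the changes concern only eligibility status and analysis. The cost is a short amendment to both documents, and follow-up of a few subjects who might otherwise be recorded as screen failures (adverse-event collection now starts at enrollment). The downside is that a few subjects treated before device entry stay in the comparison and add a little noise.
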